6.1.3 Day 1 Visit

Day 1 visit will occur within 24 hours of experiencing signs or symptoms of a cold sore. The patient will start applying study drug as soon as they notice signs or symptoms of a cold sore. The subject will present for a follow up appointment in clinic or via virtual video call consisting of:

- Review of the subject's diary card to identify possible treatment emergent adverse events.
- Assessment of the subject's pain on a visual analog scale.
- Measurement of the lesion will be taken (if lesion is present).
- Photographs of area exposed to UV radiation may be asked to be taken by subjects and uploaded into their MyChart account. If patients are present in clinic, photographs will be taken by study staff.
- If the subject has experienced a prodrome or lesion they should have started dosing. The study staff will review their dosing compliance and examine the study product tube/bottle. If the subject is not complying with the dosing regimen, the study staff will determine whether non-compliance is serious enough to warrant terminating the subject's participation. Otherwise, minor non-compliance should be noted, and the subject should be retrained on how to dose themselves.

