Patients will be called daily by the study team after their induction visit to determine the start of prodrome. When the patient first senses the prodromal phase, they need to be seen within 24 hours for the Day 1 visit. Patients that do not have prodromal senses within 7 days of the induction will be considered induction failures. Induction failure patients will be asked to return their study drug to the study team.

On Days 1, 3, 5, and 7 the subject will follow up in person or via virtual MyChart visit with blinded assessor during which the subject's diary card will be reviewed and compliance with dosing checked. If the subject has noted any unusual symptoms, these will be discussed with medical personnel to determine if a treatment emergent adverse event has occurred or, if the subject has not started treatment, whether their medical history should be updated. If possible, the lesion will be measured. A photo will be taken of the irradiated area (as marked at the induction visit). More study drug may be dispensed as needed. Most subjects' lesions will have resolved by day 7, and they will end study treatment after 7 full days of

treatment. If lesion has not resolved by day 7, the maximum number of days the patient may use study drug treatment is 10 days. An end of study (EOS) visit will occur as soon as their lesion is healed or Day 10, whichever comes first.

The EOS visit (Day 10) is expected to be the final study visit. EOS will occur when a subject's lesion is fully healed or Day 10 (whichever comes first). A photo will be taken of the irradiated area, the diary card will be carefully reviewed and study product (including empty containers) will be collected. Subjects who developed a lesion that has not yet healed will be given the option to begin taking a prn medication that has been previously prescribed to treat an outbreak.

If an adverse event has occurred but has not resolved by the EOS visit, the subject will be contacted once weekly, and status of the AE noted until such time as the event has resolved.

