6.1.4 Study Days 3, 5, and 7 Visits

On Days 3, 5, and 7, the subject will present for a follow up appointment in clinic or via virtual video call consisting of:

- Review of the subject’s diary card to identify possible treatment emergent adverse events.
- Assessment of the subject’s pain on a visual analog scale.
- Measurement of the lesion will be taken (if lesion is present).
- Photographs of area exposed to UV radiation may be asked to be taken by subjects and uploaded into their MyChart account. If patients are present in clinic, photographs will be taken by study staff.
- If the subject has experienced a prodrome or lesion they should have started dosing. The study staff will review their dosing compliance and examine the study product tube/bottle. If the subject is not complying with the dosing regimen, the study staff will determine whether non-compliance is serious enough to warrant terminating the subject’s participation. Otherwise, minor non-compliance should be noted, and the subject should be retrained on how to dose themselves.

Once patients reach the Stage 2/3 lesion their lesion may be swabbed for viral culture (HSV PCR). If the patient reaches Stage 2/3 over the weekend, the lesion will not be swabbed. We will reserve this for the first five patients but may continue to do all patients to ensure lesion is in fact a cold sore and not a reaction to the UV radiation.

6.1.5 EOS – End of Study Visit (Day 10 – or after subject’s lesion has fully healed)

An EOS visit will occur after the subject’s lesion has fully healed or Day 10 (whichever comes first), the subject will present to the clinic for a follow up appointment in clinic or via virtual video call consisting of:

- Review of the subject’s diary card to identify possible treatment emergent adverse events. If the subject has an AE that has not resolved by this time, the site staff will explain to the subject that they will be called every week to check on the status of the AE, until it is resolved.
- Assessment of the subject’s pain on a visual analog scale.

- Photographs of area exposed to UV radiation may be asked to be taken by subjects and uploaded into their MyChart account. If patients are present in clinic, photographs will be taken by study staff.

The subject's diary card and all tubes//bottles of study product (empty, partially used or unused) will be collected and the subject will be released from the study.

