7. EFFICACY EVALUATIONS

7.1 Number of subjects that experience prodrome (Stage 1) but do not progress to vesicles (Stage 3) by completion of treatment

The Principal Investigator or his designee will review all photographs taken from Day 1 through the EOS visit against the onset of prodrome date and the date of healing or 7 full days of treatment noted on the subject's diary card. They will then determine the duration of the HSV outbreak (prodrome to healed). This may or may not agree with the subject's assessment of "healed" but should be based on the collective information gathered during the subject's time on study. The blinded assessor will assess the prodrome and/or lesion at every clinic visit starting at day 3. The blinded assessor will only be responsible for the rating of the prodrome and or/lesions. The blinded assessor will not be performing safety evaluations. The unblinded staff will instruct the subject to not talk with the blinded assessor about which treatment they have been using.

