10. SCHEDULE OF ASSESSMENTS

ASSESSMENT	SCREENING	Induction Visit	Daily after induction visit to Day 1	DAY 1	DAY 5	DAY 7	DAY 10/ EOS	Follow -up phone call (EOS +2 days)
Informed Consent	X							
Medical/HSV History	X	X (med hx only)						
Urine Pregnancy Test (for woman of child bearing potential only)	X							
Limited Physical Exam	X	X						
Concomitant Medications	X	X						X
UV susceptibility test / MED testing	X (exposure)							
MED Reading		X						
Randomization		X						
UV exposure at 3 x MED (cold sore inducing)		X						
Study Product Dispensed		X						
Dosing Begins				X				
Dosing Ends						X		
Collect Study Product (including empty tubes/bottles)							X	
Photograph of irradiated area and lesion may be taken		X		X	X	X	X	X
Measurement of lesion (if possible)				X	X	X	X	X
Dispensing of Diary Card		X						
Review of Diary Card/Dosing compliance				X	X	X	X	
Solicitation of Adverse Events			X	X	X	X	X	X
Rating of lesion by blinded assessor				X	X	X	X	
Phone call to check for prodromal senses			X

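### Lesion photographs are required in Section 3 but optional at video visits in Section 6, so the Section 7.1 duration review can have no images to work from

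*Combined protocol and SAP*

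**What the plan says.** The documents give two answers on photographs between Day 1 and EOS.

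**Required.** Section 3 covers Days 1, 3, 5 and 7 together, whether attended in person or through MyChart, and states "A photo will be taken of the irradiated area (as marked at the induction visit"), with no exception for video. It requires one at EOS as well. The Synopsis uses the same mandatory wording for Day 1, for Days 3, 5 and 7, and for EOS.

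**Optional when remote.** Sections 6.1.3, 6.1.4 and 6.1.5 each say "Photographs of area exposed to UV radiation may be asked to be taken by subjects and uploaded into their MyChart account", and then "If patients are present in clinic, photographs will be taken by study staff". The Section 10 row is titled "Photograph of irradiated area and lesion may be taken" and does not separate clinic from video.

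**Visit mode.** Sections 6.1.3 and 6.1.4 allow Days 1, 3, 5 and 7 to be held in clinic or by video. Section 6.1.5 does the same for EOS: "the subject will present to the clinic for a follow up appointment in clinic or via virtual video call". Section 6.1.2 books Day 3 as a video call.

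**Use of the images.** Under Section 7.1 the Principal Investigator or a designee "will review all photographs taken from Day 1 through the EOS visit" against the prodrome and healing dates in the diary, and then sets the length of the outbreak. The result may differ from the subject's own view of healing, and it is to draw on everything collected about that subject. Section 3 says that the subject and the Principal Investigator know the treatment. Section 9.2 compares episode duration by t-test and assesses time to healing by Kaplan-Meier methods.

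**The concern.** Section 7.1 treats the photographs as the check on the diary. The visit sections, which site staff will follow day to day, allow that check to be absent for a whole subject without any deviation from those sections.

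The subject knows the treatment, and so does the Principal Investigator. Without images, the healing date comes mainly from the subject's diary and from what was seen live on video, and it may be settled by someone who knows the arm. A stored, dated image is the one lesion record in the visit sections that someone unaware of treatment could read again later.

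The results at stake are the secondary ones on episode duration and time to healing. EOS is the weakest visit in this respect. Section 6.1.5 lists diary review, pain and photographs, but neither a lesion measurement nor a blinded rating, although the Synopsis and Section 10 include both. In that section the photograph is the only direct record of the lesion, and by video it is optional.

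**Working it through.** The plan states no figure on this point, so the check is a count of the photographs that each part of the protocol guarantees per subject.

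**Inputs**
- Assessment visits: Days 1, 3, 5 and 7 (4) plus EOS (1), so 4 + 1 = 5. There are fewer if the lesion heals early and EOS is brought forward (Section 3, Section 6.1.5).
- Visits that may be by video: all 5 (Sections 6.1.3 to 6.1.5).
- Section 3 and Synopsis: a photograph at every one of these visits.
- Section 6: a photograph at clinic visits only.
- Section 10: no visit at which a photograph is compulsory.

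**Count.** Let *v* be the number of a subject's five visits held by video. Section 3 guarantees 5, Section 6 guarantees 5 − *v*, and Section 10 guarantees 0.

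| Subject | Synopsis and Section 3 | Section 6 | Section 10 |
|---|---|---|---|
| All in clinic (*v* = 0) | 5 | 5 − 0 = 5 | 0 |
| Day 3 only by video (*v* = 1) | 5 | 5 − 1 = 4 | 0 |
| All by video (*v* = 5) | 5 | 5 − 5 = 0 | 0 |

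These counts are for a subject who attends all five visits; with early healing each is an upper limit. For a subject seen only by video, the set of images that Section 7.1 reviews can therefore be empty.

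**Which results this reaches.** Section 7.1 is headed with the primary endpoint, but its text on photographs yields only outbreak duration. Staging is a separate task. Section 7.1 gives the rating of prodrome and lesion to the blinded assessor, and Section 3 places that assessor at the Day 1, 3, 5 and 7 visits whether in person or virtual. Section 10 has its own row for the blinded rating. A missing photograph therefore affects the duration and healing analyses in Section 9.2. It does not make Stage 3 status missing.

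**The case against.** The case on the other side is substantial, and much of it stands.

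- *Photographs are not optional everywhere.* Section 6 makes them compulsory in clinic. This stands: the gap in Section 6 is confined to video visits, although every visit may be one.
- *Photographs are one source among several.* Section 7.1 weighs them with the diary and the other information collected. This stands too. Their absence weakens the determination of duration but does not make it impossible.
- *Section 3 already requires them.* True, and it means the intent is probably mandatory. But Section 3 and Section 6 are both current text, and they cannot both be followed as written.
- *This is a small pilot, and the affected endpoints are secondary.* This limits the weight of the point. It does not argue against a correction that costs almost nothing.

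A reader might also infer more than the documents support:

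- That each subject without images costs the primary proportion 10 percentage points, taking 10 per arm (1/10). A missing image does not remove a subject from that proportion, because the blinded assessor still rates the stage. Ten per arm is itself an assumption: the 20 completers are a total, and Section 4.3 specifies simple randomization.
- That unblinded staff choose who is photographed. Section 6 does not say who makes the request.
- That images will be available more often in one arm. This is possible in an open-label setting, but the documents give no mechanism, so it is a risk and not a demonstrated bias.

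**Conclusion.** The point holds as an internal contradiction with a limited but real consequence. For a subject seen only by video, the protocol guarantees up to five photographs in one place and none in two others, while Section 7.1 relies on them as an input to outbreak duration. If Section 6 is followed, the episode-duration and time-to-healing results for such a subject rest mainly on an unblinded diary and what was seen on video. The primary endpoint loses a record that could be verified, not its rating, and no figure stated in the plan changes.

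The practical size depends on how many visits are held by video and how often staff ask for an image. The documents give neither, so the count above is what the text permits, not a forecast.

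**What to change.** 1. In Sections 6.1.3, 6.1.4 and 6.1.5, require a dated photograph at every visit from Day 1 to EOS, taken by staff in clinic and uploaded by the subject to MyChart when the visit is by video. This brings Section 6 into line with Section 3.
2. Make the Section 10 row match for Days 1, 3, 5, 7 and EOS only. The row also marks the Induction Visit and the follow-up phone call, so a blanket change of wording would go too far: the induction photograph should stay optional, and none should be required at the call. The table as available shows no Day 3 column; if that is so in the source, add one.
3. Amend Section 7.1 so that the existing blinded assessor reads the photographs to set the healing date, and say which record is used when a photograph is still missing. Without this change the images would still be read by the Principal Investigator, who is unblinded, or a designee.

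The cost is wording in five places, about five phone photographs per subject, and a little more reading time for the blinded assessor. The MyChart account is already set up at screening (Section 6.1.1). Because the comparator is a white cream and EED is clear (Section 3), subjects should be asked for images with no product visible; otherwise the photograph could reveal the arm.

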6.1.4 Study Days 3, 5, and 7 Visits

On Days 3, 5, and 7, the subject will present for a follow up appointment in clinic or via virtual video call consisting of:

- Review of the subject’s diary card to identify possible treatment emergent adverse events.
- Assessment of the subject’s pain on a visual analog scale.
- Measurement of the lesion will be taken (if lesion is present).
- Photographs of area exposed to UV radiation may be asked to be taken by subjects and uploaded into their MyChart account. If patients are present in clinic, photographs will be taken by study staff.
- If the subject has experienced a prodrome or lesion they should have started dosing. The study staff will review their dosing compliance and examine the study product tube/bottle. If the subject is not complying with the dosing regimen, the study staff will determine whether non-compliance is serious enough to warrant terminating the subject’s participation. Otherwise, minor non-compliance should be noted, and the subject should be retrained on how to dose themselves.

Once patients reach the Stage 2/3 lesion their lesion may be swabbed for viral culture (HSV PCR). If the patient reaches Stage 2/3 over the weekend, the lesion will not be swabbed. We will reserve this for the first five patients but may continue to do all patients to ensure lesion is in fact a cold sore and not a reaction to the UV radiation.

6.1.5 EOS – End of Study Visit (Day 10 – or after subject’s lesion has fully healed)

An EOS visit will occur after the subject’s lesion has fully healed or Day 10 (whichever comes first), the subject will present to the clinic for a follow up appointment in clinic or via virtual video call consisting of:

- Review of the subject’s diary card to identify possible treatment emergent adverse events. If the subject has an AE that has not resolved by this time, the site staff will explain to the subject that they will be called every week to check on the status of the AE, until it is resolved.
- Assessment of the subject’s pain on a visual analog scale.

- Photographs of area exposed to UV radiation may be asked to be taken by subjects and uploaded into their MyChart account. If patients are present in clinic, photographs will be taken by study staff.

The subject's diary card and all tubes//bottles of study product (empty, partially used or unused) will be collected and the subject will be released from the study.

6.2 Early Discontinuation Visit

If at any time during the study, a subject wants to stop participating or the Investigator believes it is in the subject's best interest to stop treatment, every effort should be made to complete the final assessments noted in the EOS visit.

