	
study medication and instructed how to apply it to the exposed area. When the patient first senses the start of developing a cold sore and applies study medication will be considered Day 1. Dosing of the study product will be done five times daily, beginning at the time that a subject first senses the start of the prodromal phase (Day 1). Subjects will be given a diary card to record their pain levels, progression of lesion development and any unusual symptoms (not normally seen with their outbreaks).
 
Patients will be called daily by the study team after their induction visit to determine the start of prodrome. If after 7 days, the patient does not develop any prodromal senses, the patient will be considered an induction failure.
 
When the patient first senses signs or symptoms of a cold sore, they will have the Day 1 visit conducted within 24 hours. Day 1 visit may be conducted in person or as a MyChart Virtual Visit. Their diary card will be reviewed and if they have experienced a prodrome and/or lesion since the induction visit, their compliance with dosing will be checked. If the subject has noted any unusual symptoms, these will be discussed with medical personnel to determine if the symptoms represent a treatment emergent AE. A photo will be taken of the irradiated area (as marked at the induction visit). The blinded assessor will assess the prodrome and/or lesion and take measurements.
 
On Days 3, 5, and 7, the subject will return to the clinic or follow up via virtual video call for assessment of the irradiated area. Study staff will review the subject diary to determine if the subject is correctly noting the lesion stage. Subjects will have a photo taken of the radiated area and asked to continue with dosing as instructed. Any diary card notation of unusual symptoms in subjects will be reviewed by study staff to determine if the symptoms represent a treatment emergent adverse event. The blinded assessor will assess the prodrome and/or lesion and take measurements. More study product may be dispensed as needed. Most subjects' lesions will have resolved by day 7, and they will end study treatment after 7 full days of treatment. If lesion has not resolved by day 7, the maximum number of days the patient may use study drug treatment is 10 days.
 
The EOS is the final study visit will take place on Day 10. A photo will be taken of the irradiated area, the diary card will be carefully reviewed and study product (including empty containers) will be collected. If subjects reach EOS without full resolution of their lesion(s), they will be given the option to begin taking a prn medication for the remainder of the outbreak. Measurements will be taken. If an adverse event has occurred but has not resolved by the EOS visit, the subject will be contacted once weekly and status noted until such time as the event has resolved. The blinded assessor will assess the prodrome and/or lesion.
 
A Safety follow-up phone call will occur 2 days after the EOS to determine if any new AEs have occurred.
 
Safety will also be evaluated by an independent physician throughout the study. The first independent safety evaluation will be done once 5 subjects

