Abreva® has been chosen as the Comparator product in this study because it is approved by the FDA for treatment of HSV-related cold sores. Dosing 5 times/day has been selected as the dosing regimen because that is the dosing regimen approved for Abreva by FDA. The manufacturers of Abreva recommend that subjects not be treated for greater than 10 days. A maximum of 7 days treatment with study product has been chosen for this study.

Thus, treatment in both groups of subjects, will be 5 times daily and will last until healing of the lesion, or up to 7 days following the onset of the prodrome.

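### Subjects whose treatment the investigator stops, or whom staff terminate for non-compliance, are not stated to stay on blinded stage rating, so their primary outcome may go unobserved and the text allows them to be left out

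*Combined protocol and SAP*

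**What the plan says.** **Stopping.** Section 6.2 covers two events in one sentence: a subject who no longer wants to take part, and an investigator who thinks it is in the subject's "best interest to stop treatment, every effort should be made to complete the final assessments noted in the EOS visit". Separately, section 6.1.3 says that for a subject who is not dosing as instructed, "the study staff will determine whether non-compliance is serious enough to warrant terminating the" subject's participation. Section 6.1.4 repeats this for Days 3, 5 and 7. No threshold for serious non-compliance is given. Minor non-compliance leads to retraining.

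**What an exit visit contains.** The list in section 6.1.5 has diary review, pain and photographs, but no stage rating. The synopsis (Design) does place one at the EOS visit: "The blinded assessor will assess the prodrome and/or lesion". The schedule in section 10 agrees. At EOS the diary is collected and the subject is released. The calls in section 6.3 ask about unusual symptoms. The schedule also marks a possible photograph and lesion measurement at EOS plus 2 days, without a blinded rating.

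**Endpoint and analysis.** The primary evaluation in section 7.1 counts subjects who have a prodrome but "do not progress to vesicles (Stage 3) by completion of treatment". Section 9.1 defines a Safety set and a Per Protocol set, the latter limited to subjects who attend every visit. Section 9.2 names no set for the primary test. Section 5 continues enrollment until 20 subjects have expressed a lesion and completed treatment.

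**Who decides.** Section 3 leaves the subject and principal investigator unblinded. On compliance, section 6.1.4 says: "The study staff will review their dosing compliance and examine the study product tube/bottle". Under sections 4.1 and 4.2 that container is a labeled dropper bottle in one arm and a tube in the other.

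**The concern.** Whether a subject reaches Stage 3 is settled over days. A subject already rated Stage 3 before stopping has a known outcome. One who is stopped between prodrome and vesicle does not, unless someone keeps looking. The protocol does not say that anyone does.

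Randomization protects the comparison only if every randomized subject who enters the outcome period is followed and counted. Here, decisions taken after randomization can settle both whether the outcome is seen and whether the subject is in the analysis. The people taking them can know the arm and can see how the lesion is going. If stopping is related to both arm and prognosis, the difference between arms shifts. If it is not, only information is lost. Staging that was never done cannot be recovered at analysis. The blinded assessor does not help with a visit that does not take place.

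**Working it through.** The plan gives no stopping rate, event rate, alpha or power, so there is no figure to reproduce. The check has a reading of the text and an illustration.

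**1. Which subjects are affected**

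- *Investigator stops treatment (6.2):* one best-effort EOS-type assessment, with no statement that later ratings continue.
- *Staff terminate for non-compliance (6.1.3, 6.1.4):* no later outcome collection is stated. Section 6.2 does not clearly cover this case.
- *Subject simply stops applying product:* not addressed. The Day 3, 5 and 7 visits are not conditional on dosing, so nothing removes this subject from follow-up.
- *Subject withdraws consent:* follow-up ends, and no redesign changes that.

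The first two groups carry the point.

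**2. The outcome window**

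Section 1.1 says "A maximum of 7 days treatment with study product has been chosen for this study", and section 7.1 refers to "the date of healing or 7 full days of treatment noted on the" diary card. Section 3 says that, for an unresolved lesion, "the maximum number of days the patient may use study drug treatment is 10 days". So the planned end may be Day 7 or Day 10, and no rule covers a subject stopped before either. Counting that subject as a non-progressor at exit, as missing, or as excluded would each be compatible with the text.

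**3. What the handling does to one arm**

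Assumptions, none from the documents: 10 subjects in the arm, true success (non-progression) rate p, k subjects stopped before a vesicle, each with chance q of later reaching Stage 3, so their own success rate is s = 1 − q. Replacements succeed at rate p and enter the same arm.

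- Counted as a success at exit: shift = 10kq points.
- Excluded and replaced: shift = 10k(p − s) = 10k(p − 1 + q) points.
- Gap between the two: 10kq − 10k(p − 1 + q) = 10k(1 − p) points, whatever q is.

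For k = 1 and p = 0.4:

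| q | s | Counted as success | Excluded and replaced | Gap |
|---|---|---|---|---|
| 0 | 1.0 | 0 | −6 | 6 |
| 0.2 | 0.8 | +2 | −4 | 6 |
| 0.4 | 0.6 | +4 | −2 | 6 |
| 0.6 | 0.4 | +6 | 0 | 6 |
| 0.8 | 0.2 | +8 | +2 | 6 |
| 1.0 | 0 | +10 | +4 | 6 |

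The gap per subject is 10(1 − 0.2) = 8 points at p = 0.2 and 10(1 − 0.6) = 4 at p = 0.6. A simulation with p = 0.4, q = 0.2, k = 2 (400,000 runs) gave 40.0% true, 44.0% counted as successes and 32.0% excluded and replaced, matching +4 and −8 from the formulas. Exclusion can therefore move an arm either way.

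If excluded subjects are not replaced, shift = 100k(p − s)/(10 − k). For k = 2 and p = 0.4 this is 200(0.4 − 0.2)/8 = +5 points at s = 0.2, and 200(0.4 − 0.8)/8 = −10 points at s = 0.8.

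**4. Bounds on the comparison**

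Assume 10 per arm, two unobserved outcomes in each, and completers at 5/8 on EED v 2/8 on the comparator (difference 37.5 points, uncorrected chi-square p = 0.13).

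- Most favorable to EED: 7/10 v 2/10, difference 50 points, p = 0.025 (Fisher 0.07).
- Least favorable: 5/10 v 4/10, difference 10 points, p = 0.65.

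**The case against.** The best defense is that the protocol does not send early stoppers away in so many words. EOS is defined as healing or Day 10, so section 6.2 can be read as asking for the assessments at that time. A reader might also infer three stronger things, and the documents support none of them.

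- *Anyone who stops using product loses follow-up.* Not supported. Visits are not tied to dosing, and minor non-compliance leads to retraining.
- *The endpoint is cut off at each subject's stop date.* This is one reading of the phrase about completing treatment. The planned course is the more natural one, given the reference to 7 full days in section 7.1.
- *Early stoppers will be excluded and replaced.* This is an inference. Section 9.2 names no set, and the 20 completers in section 5 are a recruitment target, not an analysis rule.

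Some later information may also exist. The EOS-plus-2-day photograph and measurement, or a recall to clinic after a section 6.3 call, could catch a late vesicle.

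The sizes are assumed. Stopping is placed in one arm in step 3, whereas equal and similar stopping in both arms would cancel in expectation. Under the simple randomization in section 4.3 a replacement can enter either arm. With 10 per arm at 40%, the standard error of the difference is √(2 × 0.4 × 0.6/10) = 0.22, or 22 points, so a shift of a few points sits well inside chance variation. This is also a pilot with a short treatment period, and few subjects may be stopped.

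What remains is narrower but stands. The heading of section 6.2 points to a visit at discontinuation, and even the Day 10 reading leaves the intermediate ratings unstated. The later calls and photographs are not blinded ratings. Non-compliance terminations have no stated outcome collection at all.

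**Conclusion.** The point holds for investigator-directed stops and non-compliance terminations before Stage 3. For these subjects the protocol provides at most one best-effort exit assessment, and not clearly even that after a non-compliance termination. It does not say that blinded staging continues, and it allows them to be left out of the primary comparison. Those decisions rest with people who can know the arm.

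Neither the size nor the direction of any bias can be stated. The 6-point change per subject (4 to 8 points for assumed success rates from 60% down to 20%) measures how far the result depends on an unwritten choice of handling. It assumes 10 per arm and same-arm replacement, and it is not an estimate of bias. If stopping is rare, or unrelated to arm and outcome, the harm is small. The change should be made because it is cheap and missing ratings cannot be recovered, not because the trial is shown to be biased.

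**What to change.** - **6.2:** separate stopping product from withdrawing consent. A subject who stops product for any reason keeps the planned Day 3, 5, 7 and 10/EOS contacts, in clinic or by video, with blinded stage rating, unless consent is withdrawn or the subject is lost.
- **6.1.3 and 6.1.4:** let staff stop product, or record the deviation and retrain, but not end outcome follow-up.
- **6.1.5:** add the blinded rating to the list, to match the synopsis and schedule.
- **7.1:** assess Stage 3 to one fixed day counted from Day 1, whenever product stopped. Day 7 or Day 10 is the sponsor's choice.
- **9.2:** report all dosed subjects who were not induction failures, as randomized, beside the Per Protocol result.
- **9.1:** say whether a subject who stopped product but attended every visit is Per Protocol. As worded, they would be.

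When to stop product, and whether stopped subjects count toward the 20, stays with the investigator and sponsor.

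The cost is protocol wording, a few extra off-product contacts of a kind already scheduled, and one analysis row. The all-dosed estimate will include imperfect adherence, and the Per Protocol result remains beside it.
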